The risk prediction models selected in Phase I will be calculated from the raw data collected in Phase II using standardised computer algorithms. Any ambiguities in the precise methods for each model will be clarified by contacting the model authors.

Models will be validated with measures of discrimination (the ability to separate survivors from non-survivors or those with favourable outcomes from those with unfavourable outcomes), calibration (the degree of agreement between the observed and predicted outcomes) and overall goodness-of-fit. If the calibration is poor, then the best model(s) will be recalibrated to provide revised coefficients specific to UK neurocritical care.

Assessment of loss to follow-up

Available data from the critical care and hospital stay will be used to compare the characteristics of responders and non-responders and to determine whether response varies by: age; severity of injury; physiological response to injury; organ monitoring

and support received in critical care; duration of stay in critical care and in hospital; destination following discharge from acute hospital; and predicted 6-month outcome.

Provided all variables associated with missing response are included in the risk model, complete case analysis of data with missing responses is statistically valid, under the assumption that data are missing at random given the observed covariates. We therefore do not propose using statistical methods for missing data such as multiple imputation unless: (1) the observed loss to follow up is considerably higher than anticipated; or (2) factors relating to processes of care (e.g. duration of critical care stay), and therefore excluded from the risk models, are found to be independent predictors of missing response.

Validation methods

Risk prediction models will be validated for discrimination, calibration and goodness-of-fit, based on methods used previously for the validation of risk prediction models for adult, general critical care^{4;5} and paediatric critical care,²⁷ and for evaluating general risk prediction models in patients with TBI.⁶

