The cost analysis will take a health and personal social services perspective.³⁵ For each admission, each day during the hospital stay will be assigned to the appropriate healthcare resource group (HRG) using daily organ support data recorded for the CCMDs. For each admission, the costs per hospital bed-day for each HRG during critical care and for each bed-day for general medical care will be taken from the Payment by Results database using trust-specific unit costs.³⁶ These unit costs will be combined with each patient's resource use data to estimate the total cost of each initial hospital admission. Information will be collected on hospital readmissions and use of community health services post discharge at six-month follow-up. The study will report the total six-month hospital and community health service costs for each case. The analysis will compare mean costs across the groups recognising any differences in either the resource use or unit costs.

The effect of location of neurocritical care on six-month mortality and unfavourable outcomes will be evaluated using multilevel logistic regression models. Using a

multilevel model (MLM) enables adjustment for both patient-level factors, including the selected risk prediction model, and unit-level factors, such as the volume of cases, the size of the unit and, most importantly, the type (specialist or general) and location (neuroscience centre or not) of the unit.

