The primary outcomes will be mortality and unfavourable outcome, defined as death, vegetative state or severe disability on Glasgow Outcome Scale (Extended), at six months following admission to critical care. The duration of follow-up has been restricted to six months for the purpose of this study as this is the primary endpoint of the existing risk prediction models, and to limit costs, however discussions with service user representatives indicate that longer-term outcomes may be important. Further list cleaning against the NHS Central Register will enable ongoing follow-up of mortality beyond six months. Secondary outcome measures will include six-month and lifetime costs and cost-effectiveness.

Proposed sample size

We performed a simulation study to assess the power to detect a difference in the c index (area under the receiver operating characteristic, ROC, curve) between two different risk prediction models applied to the same population. Simulations were based on the following assumptions: the rate of unfavourable outcomes in the population will be 40% (based on the observed rate of unfavourable outcomes in high income countries in the CRASH trial,¹¹ and consistent with the results of a regional audit in East Anglia³⁹); statistical tests will be based on a two-sided p-value of $P=0.05$; we wish to be able to detect, with 80% power, a 10% relative difference in c index from the value of 0.83 observed for the CRASH model in the development sample.¹¹ A total of 17,500 datasets were simulated at different sample sizes using a binormal model⁴⁰ and the empirical power was assessed at each sample size as the proportion of datasets in which a statistically significant difference was detected (see Appendix 3).

Based on these simulations, a sample size of 3100 patients will be required for model validation. To allow for 8% loss to follow-up (based on the observed follow-up rates from CRASH and RESCUEicp), we will aim to recruit 3400 patients.

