Using data from the Case Mix Programme Database, we anticipate the rate of admission of patients with TBI to be approximately 8 per unit per month for neurocritical care units, 6 per unit per month for general critical care units within a neuroscience centre, and 0.5 per unit per month for general critical care units outside a neuroscience centre. We will therefore aim to recruit at least 12 neurocritical care units, 13 general critical care units within neuroscience centres and 30 general critical care units outside neuroscience centres to complete recruitment within 18 months.

ORGANISATION

Study Steering Group

The Study Steering Group (SSG) responsibilities are to approve the study protocol and any amendments, to monitor and supervise the study towards its research objectives, to review relevant information from external sources, and to resolve problems identified by the Study Management Group. Face-to-face meetings will be held at regular intervals determined by need and not less than once a year, with routine business conducted by telephone, email and post. The SSG membership is shown below and terms of reference are given in Appendix 4. Representatives of the funder (NIHR HTA Programme) and the sponsor (ICNARC) will be invited to observe at SSG meetings.

Membership

[name] (Independent Chair)	Director, Centre for Anaesthesia UCL
[name] (Chief Investigator)	Statistician, Intensive Care National Audit & Research Centre (ICNARC)
[name] (Co-investigator)	Lecturer in Health Economics, London School of Hygiene and Tropical Medicine
[name] (Co-investigator)	Senior Surgical Scientist, Academic Neurosurgery Unit, University of Cambridge
[name] (Co-investigator)	Research Director, Trauma Audit and Research Network (TARN)
[name] (Co-investigator)	Professor of Anaesthesia, University of Cambridge
[name] (Co-investigator)	Director, ICNARC
[name] (Co-investigator)	Consultant in Neuroanaesthesia and Neurocritical care, The National Hospital for Neurology and Neurosurgery

[name] (Co-investigator)	Consultant in Adult Critical Care, Queen's Medical Centre, Nottingham
[name] (Independent)	Clinical Research Registrar in Neurosurgery, Nuffield Department of Surgery, Oxford
[name] (Independent)	Consultant Anaesthetist, The Walton Centre for Neurosurgery, Liverpool
[name] (Service User Representative)	Headway UK, London

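### The non-response check does not name unit type or location, and its loss trigger cannot register poor follow-up in the small outside-centre group, so the Phase IV comparison of unfavourable outcome and cost-effectiveness could be biased without being tested

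*Protocol*

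**What the plan says.** Under Assessment of loss to follow-up (Phase III), the protocol will use data from the critical care and hospital stay "to determine whether response varies by: age; severity of injury; physiological response to injury", then organ monitoring and support, and finally "duration of stay in critical care and in hospital; destination following discharge from acute hospital; and predicted 6-month outcome". Unit type and neuroscience-centre location do not appear. Discharge destination does, but it is where the patient went afterwards, not where critical care was given.

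The same section justifies its default: "Provided all variables associated with missing response are included in the risk model, complete case analysis of data with missing responses is statistically valid", assuming data missing at random given the covariates. Methods such as multiple imputation are held back unless one of two conditions is met. The first is that "the observed loss to follow up is considerably higher than anticipated"; no figure is attached and no reading by location is given. The second concerns "factors relating to processes of care (e.g. duration of critical care stay), and therefore excluded from the risk models", if these independently predict missing response.

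Under Phase IV, "The effect of location of neurocritical care on six-month mortality and unfavourable outcomes will be evaluated using multilevel logistic regression models", and type and location of unit are singled out as the most important unit-level terms. Under Phase II, deaths are checked against the NHS Central Register before anyone is contacted. Disability and EQ-5D come from questionnaires, then telephone interview, and for unfavourable outcome finally from treating teams. Under Proposed outcome measures, death counts as an unfavourable outcome.

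**The concern.** The protocol fixes three things together: what response is tested against, the default analysis, and what would change that default. The factor that matters most for Phase IV is absent from the first, and the third is not read by location.

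The design also makes inclusion in a complete-case analysis depend on outcome. A patient who dies is always counted, and counted as unfavourable. A survivor is counted only if someone reports on them. If survivors from one type of unit respond less often, deaths take a larger share of that unit type's analysed patients, and its unfavourable-outcome rate rises with no real difference in care. QALYs, and costs based on the follow-up questionnaire, are open to the same selection. These are the results meant to inform where patients with brain injury should be treated.

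A gap in response is conceivable from the text. One follow-up route, the neurocritical care follow-up service, is used only where it exists, and patients never treated in a neuroscience centre may have less access to it. The documents do not show that such a gap will occur.

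**Working it through.** **1. The plan's own figures.** Recruitment target: 3,100 / 0.92 = 3,370, rounded up in the plan to 3,400 ("To allow for 8% loss to follow-up (based on the observed follow-up rates from CRASH and RESCUEicp), we will aim to recruit 3400 patients"). Units x monthly rate x 18 months, from Proposed sample size:
- dedicated neurocritical care: 12 x 8 x 18 = 1,728
- general, within a centre: 13 x 6 x 18 = 1,404
- general, outside a centre ("0.5 per unit per month for general critical care units outside a neuroscience centre"): 30 x 0.5 x 18 = 270
- total 3,402, which agrees with 3,400. The outside-centre share is 270 / 3,402 = 7.9%.

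**2. What the loss trigger can see.** Pooled loss = (270 x L + 3,132 x 0.08) / 3,402, where L is the share of all outside-centre patients lost and 8% are lost elsewhere.

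| Outside-centre loss | Pooled loss |
|---|---|
| 20% | 304.56 / 3,402 = 9.0% |
| 30% | 331.56 / 3,402 = 9.75% |
| 50% | 385.56 / 3,402 = 11.3% |

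For pooled loss to reach 12%, outside-centre loss would have to be (408.24 - 250.56) / 270 = 58%.

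**3. Bias when loss is unrelated to disability.** Assumptions: no true location effect; 40% unfavourable everywhere (the plan's figure); mortality m = 25% (not in the protocol); deaths always known; survivor response r. Observed unfavourable rate = [m + (0.40 - m) r] / [m + (1 - m) r].
- r = 0.92: 0.388 / 0.940 = 41.3%
- r = 0.80: 0.370 / 0.850 = 43.5%; odds ratio against r = 0.92 is (0.370 / 0.480) / (0.388 / 0.552) = 1.10
- r = 0.60: 0.340 / 0.700 = 48.6%; odds ratio (0.340 / 0.360) / (0.388 / 0.552) = 1.34

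At mortality of 20% to 30% the spurious difference is 1.8 to 2.7 points for 92% v 80%, and 6.0 to 8.5 points for 92% v 60%. In the second case total loss is 0.75 x (3,132 x 0.08 + 270 x 0.40) / 3,402 = 7.9%, which is the loss the plan expects.

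**4. Does risk adjustment remove it?** In a simulation with no true location effect, adjusting for a risk score with c index about 0.84, the adjusted odds ratio for location was 1.08 at 80% response and 1.29 at 60%, against 92% elsewhere. The bias shrinks slightly but remains.

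**5. Bias when loss depends on disability.** Keep 92% v 60% survivor response overall, but let disabled survivors be lost k times as often as recovered ones. With survivor loss S, the loss among recovered survivors is q = 0.75 S / (0.60 + 0.15 k), and the odds of unfavourable outcome are [0.25 + 0.15 (1 - kq)] / [0.60 (1 - q)].

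| k | Odds elsewhere (S = 0.08) | Odds outside (S = 0.40) | Odds ratio |
|---|---|---|---|
| 0.5 | 0.720 | 1.100 | 1.53 |
| 1 | 0.703 | 0.944 | 1.34 |
| 2 | 0.679 | 0.750 | 1.11 |
| 3 | 0.662 | 0.633 | 0.96 |

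The direction is therefore not fixed.

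**The case against.** **Location is in the Phase IV model.** Unequal response by location does not by itself bias a model that contains location; loss must also depend on outcome. That is correct, and if inclusion depended only on location and measured risk there would be no bias. Here, however, register deaths are always included and survivors are not, so inclusion does depend on outcome.

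**The gap might be noticed anyway.** Appendix 4 has the steering group monitor follow-up rates, including at sites that depart from the protocol. The second trigger might be read to cover place of care. Organ support, stay and discharge destination may partly track location. So a reader who infers that a location gap must pass unseen goes too far. What stands is that steering-group monitoring leads to no analysis rule, and that the second trigger neither names location nor is supplied with a test of it.

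**Follow-up is central and persistent.** Every patient gets the same sequence of GP contact, mailings and telephone calls. Nothing in the protocol suggests 40% survivor loss outside centres, so 92% v 60% is an extreme case.

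**Stronger readings.** A reader might infer that the comparison will be biased against outside-centre units. Step 5 of the working shows that the direction depends on who is lost. A reader might also infer a false-positive rate near 48% for outside-centre against dedicated units. That figure comes from the extreme case and a simple two-proportion test that ignores clustering, whereas the protocol plans a multilevel model. It should not be relied on.

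**This belongs in an analysis plan.** Often it would, and the section sits under model validation. But the protocol has already set out the factors, the default and the triggers, so the point concerns a stated rule rather than missing detail.

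**Conclusion.** The point holds in limited form. Unit type and location are not named in the response check, and the loss trigger, having no reading by location, is in practice blind to a group that makes up 7.9% of patients. Differential survivor response by location could go untested and could bias the Phase IV comparison of unfavourable outcome, QALYs and costs. The mortality comparison, which can rest on the register, is largely unaffected.

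The bias is modest in the milder scenario and material in the extreme one. It can grow, nearly vanish or reverse according to which survivors are lost. The sizes rest on assumed mortality, assumed response by location and an assumed relation between loss and disability, none of which the protocol gives. No size was calculated for QALYs or costs. The documents support a gap in the safeguards, not a prediction that the location result will be wrong.

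**What to change.** In Assessment of loss to follow-up:
- Add unit type and location (three groups) to the factors compared between responders and non-responders.
- Report response among survivors by location.
- Judge the loss trigger within each location group as well as overall.
- State that, if survivor response differs by location after adjustment for baseline factors, the unfavourable-outcome and cost-effectiveness comparisons will use inverse-probability-of-response weighting, or multiple imputation among survivors, with location in the response or imputation model.

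The check would be informative: comparing 270 with 3,132 patients, a two-sided 5% test (pooled-variance z test) has about 88% power to detect 14% v 8% loss. Clustering by unit is ignored, so true power is somewhat lower. The data needed are already collected. The cost is a few lines of text and, if the trigger is met, a little more analysis and slightly wider intervals.

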Delivery of neurocritical care for traumatic brain injury in the NHS

In the NHS, adult patients with TBI are rarely managed by a single service; they are managed by a succession of services from first contact to definitive critical care, definitive critical care not always being provided in a dedicated neurocritical care unit. Despite guidelines recommending that all patients with severe TBI be treated within a neuroscience centre,¹⁹ many (particularly those without surgical lesions) are currently neither treated in nor transferred to one. A combination of geography, bed availability, local variation and clinical assessment of prognosis can often determine the location of definitive critical care for an adult patient with TBI. The Neurocritical Care Stakeholder Group, established to offer expert advice to Department of Health and Commissioners, indicated in their audit report that, within the NHS, only 67% of beds ring-fenced for neurocritical care were in dedicated neurocritical care units and that neurocritical care unit occupancy rates exceeded 90% (especially for Level 3 beds).²⁰ Most neurocritical care for adult patients with TBI was delivered either in dedicated neurocritical care units (42%) or in general critical care units within a neuroscience centre (35%). However, despite clear guidelines and the progressive regionalisation of neurosurgical care since 1948, 23% of patients with TBI were treated in general critical care units outside a neuroscience centre. Local critical care consultant opinion indicated at least 83% of these patients required transfer to a neuroscience centre. No data were available, or are routinely collected, within the NHS for risk-adjusted comparisons.

Where adult patients with TBI should be optimally treated is an important question for the NHS, both in terms of outcomes and costs. Belief and limited evidence has underpinned the establishment, and continuing expansion, of dedicated, neurocritical care facilities in the UK^{21;22} but no formal evaluation has been undertaken. Recent research has suggested benefit from managing severe head injury in specialist centres,²³ however this is acknowledged to be inconclusive due to lack of adjustment for all known confounders and the use of an unvalidated risk prediction model. It also does not address the issue of general versus specialist critical care units within neuroscience centres. Research is required to determine which location(s) for

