neurocritical care are associated with improved outcomes for adult patients with TBI, particularly for those who do not require surgical intervention (external ventricular drain and/or craniotomy/craniectomy), a NICE recommendation for future research in their recently revised guideline.¹⁹ A key issue for policy-makers is whether the additional initial costs of more specialised care are justified by subsequent reductions in morbidity costs and/or improvements in patient outcomes. While conventional RCT methodology may be impractical in this setting, the presence of variation in the way services are organised and delivered can allow them to be compared using observational methods. This is only possible if a valid, reliable, appropriate and accurate risk prediction model exists.

At its inaugural meeting in February 2007, the newly formed Neurocritical Care Network (NCCNet), a network of units and staff providing neurocritical care to patients in both dedicated and general units, identified pursuing funding and establishing a risk prediction model to investigate and evaluate the location and outcomes of care for adult patients with TBI as their first, and top, priority. It was recognised that this aim could only be achieved through validation of an accurate risk prediction model for adult patients with TBI. The Society of British Neurological Surgeons, the Neuroanaesthesia Society of Great Britain and Ireland, the Intensive Care Society and the Association of British Neurologists, through the auspices of the Neurocritical Care Stakeholder Group, are all supportive of this.

STUDY DESIGN

The project will be divided into four phases, detailed below:

- Phase I: Identification of suitable models and definitions of dataset (objective 1; months 1–4)
- Phase II: Data collection and data validation (objective 2; months 5–29)
- Phase III: Validation of risk prediction models (objective 3; months 25–32)
- Phase IV: Evaluation of location of neurocritical care (objectives 4–6; months 19–36)

The flow of patients through the project is shown in Appendix 1.

Phase I: Identification of suitable models and definitions of dataset

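### The rule for costing the initial admission gives neurosurgical operations no separate cost, which probably understates neuroscience-centre costs unless the bed-day rates already include theatre

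*Protocol*

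**What the plan says.** The costing rule is in the Protocol, Phase IV: Evaluation of location of neurocritical care. The viewpoint is stated first: "The cost analysis will take a health and personal social services perspective". Days are then classified: "each day during the hospital stay will be assigned to the appropriate healthcare resource group (HRG) using daily organ support data recorded for the CCMDs". The prices named are "the costs per hospital bed-day for each HRG during critical care and for each bed-day for general medical care", and their source is the "Payment by Results database using trust-specific unit costs". The result is described as follows: "These unit costs will be combined with each patient's resource use data to estimate the total cost of each initial hospital admission".

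Two statements in the Background (Delivery of neurocritical care for traumatic brain injury in the NHS) bear on this. Of patients with severe injury who, under the guidelines, should be in a neuroscience centre, it says "many (particularly those without surgical lesions) are currently neither treated in nor transferred to one". It also singles out for research "those who do not require surgical intervention (external ventricular drain and/or craniotomy/craniectomy"), so it recognises that some of this population is operated on and some is not.

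**The concern.** The protocol does more here than leave a cost list for later. It states a formula and calls its product the total cost of the admission. The formula has no term for theatre time or a neurosurgical procedure, and organ support is not a marker of surgery. If surgery is more common in one location than another, the missing component differs between the groups being compared.

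The Background treats the extra initial cost of specialised care, and whether later benefit justifies it, as a central policy question. A differential gap in the initial cost would pass into the incremental costs and net benefits at six months. It would also pass into the lifetime projection, which extrapolates from the six-month results.

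**Working it through.** The protocol states no figure on this point, so there is none to reproduce. The check has three parts.

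**1. The rule applied to two patients.** Take two patients in the same unit, each with 8 critical care days of identical organ support and 12 ward days (numbers chosen for illustration). One has a craniectomy and an external ventricular drain; the other has no operation. Let *c* be the critical care bed-day price for that level of support and *w* the ward bed-day price.

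- Operated: 8*c* + 12*w*
- Not operated: 8*c* + 12*w*

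The two costs are identical. An operation changes the cost only if it changes the number of days or the organ support. This shows insensitivity within a unit. A difference between locations needs part 3 as well.

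**2. Does another section supply the missing item?**

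- *Phase II, health services questionnaire:* covers services used after leaving hospital, so it does not reach operations during the index stay.
- *Phase IV, other cost data:* readmissions and community services after discharge.
- *Phase II, examples of data items:* no operation is listed. The list is open-ended, so this is consistent with the gap but does not prove it.
- *Phase IV, sensitivity analysis:* described as testing model specification; missing cost components are not named.

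No section adds an operation cost.

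**3. Size of a differential omission.** For neuroscience centre versus outside, before risk adjustment:

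understatement of the cost difference per patient = *C* × (*p*in − *p*out) × (1 − *s*)

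Here *C* is the cost per operation, *p*in and *p*out are the proportions operated inside and outside neuroscience centres, and *s* is the share of operation cost already inside the bed-day rates. The protocol gives none of these. The Background supports only the sign of *p*in − *p*out. Assumed inputs: *C* £3,000 to £8,000; *p*in 0.20 to 0.40; *p*out 0.02 to 0.05.

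| Case | *s* = 0 | *s* = 0.5 | *s* = 1 |
|---|---|---|---|
| Low: £3,000 × (0.20 − 0.05) | £450 | £225 | £0 |
| Middle: £5,000 × (0.30 − 0.05) | £1,250 | £625 | £0 |
| High: £8,000 × (0.40 − 0.02) | £3,040 | £1,520 | £0 |

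The low and high rows are the extremes of the assumed ranges.

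**The case against.** The strongest reply is that the content of the trust-specific rates is unknown. They come from a cited source that the protocol does not summarise, and the resource use data are not itemised. If the rates already carry theatre cost, the average omission may be nil. This stands. A reader might infer from the rule that operations cost nothing in the analysis; the protocol does not support that. It supports only that they add no separate line.

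A reader might also infer that the bias always favours specialist location. That goes too far as well. The Background gives a direction for inside versus outside a neuroscience centre, but none for dedicated versus general units within a centre, and none for extracranial surgery. Trust-specific prices may carry some of the higher cost of neuroscience centres into the estimate.

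Risk adjustment is a further reply. The candidate models include CT classification and epidural haematoma, so part of the difference in surgical case mix may be adjusted away, and the crude figures above may be too large. This stands in part. Adjustment cannot restore a cost that was never measured. If location alters the chance of operation for similar patients, the cost of those operations belongs to the effect being estimated.

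The phrase about general medical bed-days may simply mean days outside critical care. It does not show that neurosurgical or rehabilitation ward days would be priced at an internal-medicine rate.

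Finally, costs are secondary outcomes, and price lists often belong in an analysis plan. But comparative cost is among the stated primary aims, and the protocol fixes the formula and names its result, so the point can properly be raised on the protocol.

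**Conclusion.** The point holds in a limited form. As written, the initial admission is costed from two kinds of bed-day, and a neurosurgical operation counts only through length of stay or organ support. Unless the bed-day rates already include theatre cost, initial costs are probably understated more in neuroscience centres than in general units outside them.

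The direction rests on the Background's remark about patients without surgical lesions. The size, £450 to £3,040 per patient before risk adjustment, rests wholly on assumed operation rates and prices. The lower limit is zero if the rates absorb theatre cost, and risk adjustment may reduce the figure in any case. The range shows that the question is worth settling; it does not estimate the bias.

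**What to change.** In Phase IV, first establish and state whether the trust-specific bed-day rates include theatre cost. Where they do not, add the cost of neurosurgical operations (craniotomy or craniectomy, external ventricular drain) and other major operations to the index-admission cost. Take operation type from a field in the RAIN dataset or from hospital procedure codes. Price days outside critical care by ward specialty where such rates exist. Add a sensitivity analysis that varies operation cost.

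This costs a few extra data fields or a linkage to procedure codes, a short price list and a check against double counting. It needs no extra patients. The dataset specification is a Phase I task, so adding the field there avoids going back to records later.
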